6.3 Online group video platform

An external online video platform (Beamfeelgood) will be used with the iRehab trial intervention. This platform will enable live streaming of the group intervention sessions. A Data Protection Impact Assessment will be completed and approved by Ulster University and Belfast HSCT to identify and minimise associated risks. The online platform is GDPR compliant, and Organisation for Review of Care and Health Apps (ORCHA) accredited. Any data that is stored, including the participant's email address, will be encrypted in accordance with NHS England guidance and storage will be NHS cloud compliant, conforming to ISO 9001/27001/27017/27018 standards and the G-Cloud (UK Government) standard.

Private groups will be created on the online platform and administrative access to these given only to approved staff in the intervention delivery team and WCTU. Administrative users will authorise participant's access to the private groups and participants will be asked for their consent to share utilisation metrics with the University of Warwick, Ulster University and Belfast HSCT.

Participants in the intervention arm will be asked to set up an account and profile where they agree to the terms and conditions of Beamfeelgood and consent to the University of Warwick, Ulster University and Belfast HSCT having access to any of their data collected through the platform. Participants may choose to use a nickname on the online platform to remain anonymous to other members.

This online video platform will collect and store data on participants attendance at classes and any answers relating to post-exercise session online poll questions. This information will be stored against the participants name and email address on Google data studio and held until the end of the trial. The iRehab team (University of Warwick and University of Ulster/Belfast HSCT) will be given access to this data as required to monitor attendance, safety and for analysis of compliance.

6.4 Data storage

All essential documentation and trial records will be stored at WCTU in conformance with the applicable regulatory requirements and access to stored information (paper and electronic) will be restricted to authorised personnel. All data will be stored in a designated storage facility within the WCTU. Electronic data will be stored on password protected university computers.

Separate records required for intervention delivery will be securely stored at Ulster University and Belfast HSCT for participants randomised to the intervention delivery arm.

All trial records and documentation related to the qualitative interviews will be stored and analysed by staff based at The Queens University Belfast. These records will not be transferred to WCTU.

6.5 Data access and quality assurance

Confidentiality will be strictly maintained and names or addresses of participants will not be disclosed to anyone other than the staff involved in running the trial. All electronic participant-identifiable information will be held on a secure, password-protected database accessible only to essential personnel. Any paper forms with participant-identifiable information will be held in secure, locked filing cabinets within a restricted area of WCTU, Ulster University, Belfast HSCT or The Queens University Belfast, wherever the activity is taking place. Participants will be identified by a participant number only where possible. The PI must arrange for retention of trial records on site in accordance with GCP and local Trust's policies for the length of time stated in the protocol. Direct access to source data/documents will be required for trial-related monitoring. For quality assurance, the data and results will be statistically checked. A full data management plan will be produced by the trial management team and statistician to outline the data monitoring checks required.

6.6 Data Shared with Third Parties

Requests for data sharing will be managed in accordance with University of Warwick/WCTU policy on data sharing. The datasets generated during and/or analysed during the current trial will be available upon request after publication of the main trial results. The publication of a trial protocol, trial results and trial data will be in line with the NIHR standard terms and will follow Warwick SOP 22: Publication & Dissemination.

6.7 Archiving

Trial documentation and data will be archived for at least ten years after completion of the trial. Trial documentation and data held by recruiting NHS sites will be stored for 10 years in line with their local trust policy.

7. STATISTICAL ANALYSIS

7.1 Power and sample size

The total sample size for iRehab will be **428 participants**. Using our primary outcome of EQ-5D-5L utility score at eight weeks, our target difference is 0.08 with a standard deviation of 0.2 (i.e. an effect size=0.4) (71). If we assume that there are on average seven therapists for the intervention delivery and a clustering effect will exist (ICC=0.01) and allowing for 30% loss to follow up (LTFU), a total of 428 (control: 197 and intervention: 231) participants will be required. This uses the Morbeek's formulation (72) and an unequal randomisation of the ratio of 1: 1.17. A difference of 0.08 on the primary outcome is a justifiable clinical effect. We will endeavour to minimise losses to follow-up. If we achieve a 15% loss to follow-up, we will be able to detect a smaller effect size (up to 0.37) at 90% power.

7.2 Statistical analysis of efficacy and harms

7.2.1 Statistics and data analysis

The main statistical analysis will be based on intention-to-treat. Data will be summarised and reported in accordance with CONSORT guidelines for RCTs. The impact of compliance on outcomes will be assessed using a CACE (complier average causal effect) analysis or other appropriate approach.

7.2.2 Statistical analysis plan

Summary of baseline data and flow of patients

Baseline data will be summarised by treatment arm, using means, standard deviations, medians, interquartile ranges for continuous variables and frequencies and proportions for categorical variables. Screening data will be summarised descriptively between the randomised patients, those ineligible and those eligible but not consented. A CONSORT diagram will be presented to show the patient flow throughout the trial (50).

Primary outcome analysis

The primary outcome will be summarised using means, standard deviations, medians and interquartile ranges. Linear regression will be used to estimate the treatment effect with 95% confidence interval, with and without adjustment for important patient-level covariates and site effect, by intention-to-treat. The impact of compliance will be assessed using CACE analysis or other appropriate approach.

Secondary outcome analysis

Secondary outcomes will be summarised using means, standard deviations, medians and interquartile ranges. Linear regression will be used to estimate the treatment effect with 95% confidence interval, with and without adjustment for important patient-level covariates and site effect.

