Intervention team: the iRehab intervention will be delivered by an intervention team of iRehab trained practitioners with expertise in the management of critical illness and specialist rehabilitation. The core team will include at least three staff members, managed centrally to deliver the intervention.

Referral to intervention: Participants randomised to the iRehab intervention will be notified by email or by telephone. The intervention delivery team will be notified by email that a participant has been randomised to the rehabilitation intervention. This email will contain relevant information needed to commence the intervention including contact details.

First intervention appointment

The first telephone or video consultation appointment will be arranged as soon as possible after the intervention team are notified of participant details and randomisation. Ideally, the participant will be contacted within one week of notification, maximum of three weeks. The participant will be helped to identify any symptoms of relevance to them in their recovery, to recommend the most appropriate components to best support their recovery. An appropriate individualised management plan will be set for each participant. An overview of the intervention programme is presented in Table 1).

Table 1 – Overview of iRehab rehabilitation programme

Timing	Session format	Content
Week 1	1-to-1 appointment, online	
 • Explain programme • Assess symptoms and identify needs • Provide Individual symptom management • Agree and start exercise and activity plan • Agree review appointments

	Independent or online group/recorded exercise session	
 Home exercise plan/attend group exercise session /access recorded exercise sessions
	Online peer support group (iRehab café)	
 Attend peer-support café
Weeks 2 to 6	1-to-1 appointment, online	
 Weekly review of symptoms and progression through treatment plans Continue needs assessment, symptom management and psychological support Continue exercise and activity plan Agree review appointments
	Independent or online group/recorded exercise session	
 Home exercise plan or attend group exercise session/access recorded exercise sessions
	Online peer support group (iRehab café)	
 Attend peer-support café

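### The trial is sized for therapist clustering in the intervention arm, but the regression in section 7.2.2 has no term for it

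*Protocol*

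**What the plan says.** Protocol section 7.1 sets the target: "our target difference is 0.08 with a standard deviation of 0.2 (i.e. an effect size=0.4"). It assumes "on average seven therapists for the intervention delivery and a clustering effect will exist (ICC=0.01"), allows for 30% loss to follow-up, cites a formula for comparing group and individual treatments, and uses "an unequal randomisation of the ratio of 1: 1.17". The result is that "a total of 428 (control: 197 and intervention: 231) participants will be required".

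Section 7.2.2 gives the analysis of the primary outcome: "Linear regression will be used to estimate the treatment effect with 95% confidence interval", run with and without adjustment for patient-level covariates and site. The secondary outcomes have the same model. The protocol names no therapist term, random effect, cluster-robust variance or partially nested model. Section 7.7 leaves additional statistical considerations to the SAP in general terms and does not mention therapists.

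On delivery, section 2.7.2 says: "The core team will include at least three staff members, managed centrally to deliver the intervention". Section 2.1 plans at least 30 hospitals.

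**The concern.** The design and the analysis make opposite assumptions about the same data. Section 7.1 says that participants who share a therapist have correlated outcomes and recruits more people because of it. The model in section 7.2.2 treats all participants as independent, given covariates and site.

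Site cannot stand in for therapist. The therapists belong to one central team and treat participants from every hospital, so therapist groups cut across sites. The version without adjustment has no grouping term at all.

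If clustering is present and left out of the model, the standard error of the treatment effect is too small. The 95% confidence interval is then too narrow and the type I error exceeds its nominal level. This affects the primary result and every secondary outcome analysed in the same way.

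**Working it through.** **Inputs from section 7.1.** Difference 0.08, SD 0.2 (d = 0.4); 197 control and 231 intervention; 30% loss; 7 therapists; ICC 0.01 in the intervention arm only. Power of 90% is stated only for the 15%-loss scenario and is assumed for the main calculation. Alpha is not stated; two-sided 5% is inferred from the 95% interval.

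**Reproducing 428.** With m participants per therapist, the design effect is DE = 1 + (m − 1) × ICC. The control number is n_c = (1.96 + 1.2816)² × SD² × (1 + DE/1.17) / difference², where (1.96 + 1.2816)² = 10.51 and SD²/difference² = 6.25.

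- No clustering (DE = 1): n_c = 10.51 × 6.25 × 1.855 ≈ 122, n_i ≈ 143, total 265; 265/0.7 ≈ 378.
- Clustering, m from randomised numbers (231/7 = 33, DE = 1.32): n_c ≈ 139.8, n_i ≈ 163.5, total 303.3; divided by 0.7 ≈ 433.
- Clustering, m from analysed numbers (about 22, DE ≈ 1.21): total about 290; divided by 0.7 ≈ 415.

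The stated 428 lies between the last two and within about 3% of each. It is reached only with the clustering allowance, which accounts for about 428 − 378 = 50 participants.

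**Standard errors at 30% loss.**

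- Analysed: 197 × 0.7 = 137.9 and 231 × 0.7 = 161.7.
- m = 161.7/7 = 23.1; DE = 1 + 22.1 × 0.01 = 1.221.
- SE with clustering: 0.2 × √(1/137.9 + 1.221/161.7) = 0.0243.
- SE without clustering: 0.2 × √(1/137.9 + 1/161.7) = 0.0232.
- Ratio: 1.050.

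**Effect on error and coverage.** Type I error = 2 × [1 − Φ(1.96/1.050)] = 2 × [1 − Φ(1.867)] ≈ 6.2%, so coverage is about 93.8%. A simulation with 200,000 runs, fitting an unclustered two-group model to partially nested data, gave 6.15%. By symmetry this is about 3.1% in each tail.

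**How it varies.**

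| Setting | Type I error |
|---|---|
| 7 therapists, ICC 0.005 (assumed), 30% loss | 5.6% (simulated) |
| 7 therapists, ICC 0.01, 30% loss | 6.2% |
| 7 therapists, ICC 0.01, 15% loss | 6.5% |
| 7 therapists, ICC 0.01, uneven caseloads (assumed split), 30% loss | 7.0% (simulated) |
| 7 therapists, ICC 0.02 (assumed), 30% loss | 7.4% (simulated) |
| 3 therapists, ICC 0.01, 30% loss | 7.9% (DE 1.529, SE ratio 1.115) |

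**Power when the clustering is modelled (7 therapists, ICC 0.01, 30% loss).**

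- Normal approximation: Φ(0.08/0.0243 − 1.96) = Φ(3.288 − 1.96) ≈ 90.8%.
- Satterthwaite degrees of freedom, in SD units: the control variance is 1/137.9 = 0.00725 on 136.9 df and the intervention variance is 1.221/161.7 = 0.00755 on 6 df. Then df = (0.00725 + 0.00755)² / (0.00725²/136.9 + 0.00755²/6) ≈ 22. The critical value is 2.07 and power from the non-central t is about 88%.

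**The case against.** **The SAP was not available.** Section 7.2.2 is an outline, random-effect structure is often settled in the SAP, and the words linear regression do not exclude a random term. This stands as a limit. A reader might infer that the final analysis will certainly miss its 5% level; the protocol alone does not show that. It does not remove the point, because section 7.2.2 is not silent. It names a model and its adjustment terms, including site, and the clustering assumed in section 7.1 is not among them.

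**The effect is small.** At the protocol's own inputs, 6.2% against 5% is modest. That stands. Much larger error rates need an ICC well above 0.01, and nothing in the protocol supports one.

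**Direction.** A reader might infer that the narrow interval favours declaring benefit. It does not: a standard error that is too small raises false findings of benefit and of harm equally.

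**Three against seven.** A reader might see a contradiction between a core team of at least three and an average of seven therapists. Three is a floor and seven satisfies it, so the three-therapist row is only a sensitivity case.

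**Who is the therapist?** Section 2.7.2 describes team delivery, with weekly one-to-one sessions, group exercise and a facilitated group café. No section assigns one therapist per participant, so a simple nested structure cannot be taken for granted. This also stands and shapes the fix.

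**Conclusion.** The point holds as an inconsistency between sections 7.1 and 7.2.2. Followed as written, the regression gives a standard error about 5% too small, a two-sided type I error of about 6.2%, and about 93.8% coverage for the nominal 95% interval.

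These figures rest on ICC 0.01, seven therapists with equal caseloads, 30% loss, a two-sided 5% level inferred from the 95% interval, and each participant belonging to one therapist. The excess is modest and symmetric. It grows with fewer therapists, uneven caseloads or better retention. Whether it reaches the final analysis depends on the SAP. The sample size itself is not at fault: 428 already contains the allowance for clustering.

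**What to change.** Amend section 7.2.2 so that the primary and secondary models account for therapist clustering in the intervention arm. One suitable form is a partially nested mixed model with a therapist random effect in the intervention arm only, a separate residual variance for each arm, and small-sample degrees of freedom. If the SAP already specifies such a model, align section 7.2.2 with it.

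Record which therapist delivered the one-to-one sessions to each intervention participant, and set a rule in advance for participants seen by more than one. Capture this during delivery, because it may be hard to reconstruct later.

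**Cost.** Wording in the protocol and, if needed, the SAP, plus one data field. No extra participants. The interval becomes somewhat wider: with seven therapists, the half-width goes from about 1.96 × 0.0232 = 0.045 to about 2.07 × 0.0243 = 0.050. Power at 30% loss is about 88% with small-sample degrees of freedom, against about 91% by the normal approximation. If power is restated, use the figure that matches the chosen degrees of freedom.

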7.3 Subgroup analyses

Subgroup analysis which are specified a priori include (a) duration of mechanical ventilation and (b) age (2, 6, 73). The primary outcome will be examined in relation to these subgroups using an interaction in the model with treatment and sub-group effect.

7.4 Interim analysis and criteria for early termination of the trial

The frequency and timing of the interim analysis will be reviewed and agreed by the DMC. Detailed stopping rules will be developed and specified in the SAP. The interim analysis will be conducted by trial statistician(s). The DMC will review unblinded interim data and make their decision to terminate the trial early based on the statistical evidence or safety concerns. The trial team will remain blinded to allocation during the trial unless necessary.

7.5 Subject population

The primary and secondary analyses will be conducted based on an all-randomised population by intention-to-treat.

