5.1.2 Serious Adverse Events (SAEs)

A Serious Adverse Event is an AE that fulfils one or more of the following criteria:

- Results in death
- Is immediately life-threatening
- Requires hospitalisation or prolongation of existing hospitalisation
- Results in persistent or significant disability or incapacity
- Is a congenital abnormality or birth defect
- Is an important medical condition or Immediate intervention was required to prevent one of the above

SAEs exempt from reporting

The following SAEs listed in Table 5 are common in the clinical population being studied and **do not** require reporting to the Clinical Trials Unit as an SAE for this trial, but will be recorded as part of follow-up data collection in the participant questionnaires or in the relevant section(s) of the CRF (such as the hospital readmission CRF):

Table 5 – Common SAEs in the clinical population being studied that are exempt from reporting

Events
Hospitalisation, or death, for pre-existing conditions e.g. respiratory exacerbation and infection, or a complication related to the initial ICU admission
Treatment, which was elective or pre-planned, for a pre-existing condition, not associated with any deterioration in condition

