7.6 Procedure(s) to account for missing or spurious data

Whilst every effort will be made to minimise missing data, it is inevitable that some data will be missing. We will monitor the level of and reasons for missingness in the primary outcome. The nature and pattern of missingness will be carefully considered. If deemed necessary, an appropriate imputation method, e.g., multiple imputation, will be applied to impute missing data. The imputed datasets will be analysed as a sensitivity analysis. Further details will be given in the statistical analysis plan.

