7.8 Health Economic Evaluation

A prospective within-trial economic evaluation, adhering to NICE Reference Case recommendations (67) will compare intervention with standard care. Healthcare resource use data will include in-patient and community care health service contacts during the six-month follow-up period, collected via trial CRFs and costed using the most recently available published reference costs. Generic HRQoL will be assessed at baseline, eight weeks and six months using the EQ-5D-5L, with responses converted to health status scores using the NICE-recommended UK value set and sensitivity analyses conducted using alternative tariffs if this is likely to be useful for decision-making (74). Patient-level QALY estimates will be calculated using the trapezoidal rule. Analyses will

explore and manage data missingness in line with the approach described in section 7.6. Every effort will be made to minimize missingness, but if appropriate, a suitable method such as multiple imputation will be used to account for missingness. Bootstrapped bivariate regression will estimate and visualize incremental cost-effectiveness ratios, acceptability curves and net monetary benefit. If findings are non-convergent at six months, we will explore the sensitivity of cost-effectiveness to extrapolation of costs and benefits beyond the trial time horizon, via a suitable decision model or parametric survival analysis model. Value of information analysis will be conducted to explore the sensitivity of health economic recommendations to additional research. Sensitivity analyses will also explore the impact of broadening the decision perspective beyond the NICE reference case to include indirect costs such as the impact on productivity. Additional secondary cost-effectiveness analyses will also explore the unit cost of any achieved reductions in fatigue or anxiety/depression resulting from the intervention.

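### Section 7.5 claims an analysis of everyone randomised, but the planned week-8 regression with sensitivity-only imputation covers only participants with an observed outcome

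*Protocol*

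**What the plan says.** Four statements in the protocol bear on who enters the primary analysis.

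- **Population (7.5):** "The primary and secondary analyses will be conducted based on an all-randomised population by intention-to-treat".
- **Outcome (7.1):** "Using our primary outcome of EQ-5D-5L utility score at eight weeks", so the endpoint is a single value at one time point.
- **Model (7.2.2):** "Linear regression will be used to estimate the treatment effect with 95% confidence interval", with and without covariates and site. Secondary outcomes get the same model.
- **Missing data (7.6):** "If deemed necessary, an appropriate imputation method, e.g., multiple imputation, will be applied to impute missing data", followed by "The imputed datasets will be analysed as a sensitivity analysis". Further detail is left to the SAP.

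Section 7.1 sets the total at 428 (197 control, 231 intervention) after a 30% allowance for loss, and also considers 15%. EQ-5D-5L is collected at baseline before randomisation, at eight weeks and at six months (2.6 and Table 3). Section 2.2.2 makes it the minimum core data set at both follow-ups.

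**The concern.** A regression on the week-8 score drops every participant without that score. The only device in the protocol that could bring them back is imputation, and section 7.6 gives imputation a secondary role and leaves its use to be decided once the missingness has been seen. The population in 7.5 and the analysis in 7.2.2 and 7.6 cannot both describe the primary result.

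Two things are at stake. First, a reader of 7.5 would take the primary estimate to cover 428 people when it may cover about 300, and the assumption that justifies leaving out the rest is nowhere stated. Second, someone who misses week 8 but completes the six-month EQ-5D-5L contributes nothing to the primary estimate, although that value carries information about the missing one. Section 7.5 extends the same claim to the secondary outcomes, so the mismatch applies there too.

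**Working it through.** **Inputs (protocol 7.1):** target difference 0.08; SD 0.2; seven therapists; ICC 0.01; 197 control and 231 intervention; loss 30%, alternatively 15%. Two-sided 5% is assumed from the 95% confidence interval. Power of 90% is assumed because it is stated only beside the 15% scenario.

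**1. Reproducing 428.** With clustering in the intervention arm only, the variance is SD² × [1/nc + (1 + (m − 1) × ICC)/nt], where m is patients per therapist. Solving for 90% power at a 1:1.17 ratio and dividing by 0.70 gives 415 to 420 when clustering is based on analysed patients (the range reflects normal or t quantiles and how the therapist variance enters). It gives 433 to 434 when m is based on randomised patients. The stated 428 lies between these, so it is consistent with 90% power after 30% loss.

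**2. Who is analysed.**

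- At 30% loss: 197 × 0.70 = 137.9 and 231 × 0.70 = 161.7, total 299.6. About 128 are not in the model.
- At 15% loss: 197 × 0.85 = 167.45 and 231 × 0.85 = 196.35, total 363.8. About 64 are not in the model.

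**3. Power on those analysed.** At 30% loss, m = 161.7/7 = 23.1 and the design effect is 1 + 22.1 × 0.01 = 1.221. SE = 0.2 × √(1/137.9 + 1.221/161.7) = 0.0243, and power is 0.908. With m = 231/7 = 33, the design effect is 1.32 and power is 0.897. The trial is sized for observed outcomes, so observed-case analysis does not leave it underpowered.

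**4. How far the two estimates could differ.** The protocol gives no figures for this, so both routes below rest on assumptions.

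- *Missing participants differ from observed ones in one arm only.* Shift = loss × difference. At 30% loss, assumed differences of 0.05, 0.10 and 0.20 give 0.015, 0.030 and 0.060, or 19%, 38% and 75% of 0.08. At 15% loss the shifts halve. At 30% loss a difference of 0.08/0.30 = 0.27 would equal the whole target.
- *Loss differs between arms, with the same utility gap in both.* Bias = difference in loss × gap. The range is 0.05 × 0.10 = 0.005 to 0.10 × 0.20 = 0.02, or 6% to 25% of 0.08. Ignoring clustering, SE = 0.2 × √(1/161.7 + 1/137.9) = 0.0232. At the top of the range, a bias of 0.02 would raise two-sided error from 5% to 13.9% or, acting against the intervention, cut power from 93.2% to 73.5%.

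The second route is unadjusted. Covariate adjustment would remove whatever part of the gap the covariates explain.

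**The case against.** The strongest reply is that intention-to-treat is widely used to mean analysed by allocated arm, which the plan does. A covariate-adjusted regression on observed outcomes is valid if missingness depends only on variables in the model. Multiple imputation is already foreseen, and the CONSORT diagram would show the numbers analysed. Much of this stands: the method is defensible. What does not stand is the all-randomised description without a stated missingness assumption. Leaving further detail to the SAP does not remove the conflict, because 7.6 has already fixed imputation as a sensitivity analysis.

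Three stronger readings are tempting and are not supported.

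- **That 30% loss is expected.** It is an allowance. Section 7.1 commits to minimising loss and considers 15%. Table 2 sets green above 90% completeness at week 8 and red below 75%, so 30% loss would be a red result on that pilot measure.
- **That the result will be biased.** The intervention arm has weekly sessions and the control arm does not, so unequal loss is plausible. But outcome follow-up is the same in both arms (2.2.2 and 6.1): reminders, assessor calls and repeated contact with priority for the core measures. Those who stop treatment are still followed.
- **That the plan imputes living utilities for participants who have died.** Table 5 lists "Hospitalisation, or death, for pre-existing conditions e.g. respiratory exacerbation and infection, or a complication related to the initial ICU admission" among common events, and the economic analysis will "explore and manage data missingness in line with the approach described in section 7.6". Neither place says that a value after death counts as missing. No mortality rate is given, deaths are notified separately (5.6 and 6.1), and such handling is ordinary SAP content. Nor does it bear on why the primary analysis is observed-case.

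**Conclusion.** The inconsistency is real and rests on the protocol's own text. Sections 7.2.2 and 7.6 produce an observed-case analysis by randomised arm, and 7.5 describes something else. At the planning allowances it would cover about 300 of 428 (30% loss) or about 364 (15% loss).

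The fault is a mislabelled population, an unstated missingness assumption, unused six-month information and a sensitivity analysis left to later discretion. Actual bias is not demonstrated. The shifts calculated above depend entirely on assumed utility gaps and assumed differences in loss, and show only why the assumption needs stating. The sample size stands. Handling of deaths should be confirmed in the SAP but is not a demonstrated protocol error.

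**What to change.** Choose one of two routes.

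- **(a) Change the primary model.** Use a repeated-measures model of EQ-5D-5L utility at baseline, eight weeks and six months, with the week-8 contrast as primary, and state the missing-at-random assumption. Participants who miss week 8 but are seen at six months then contribute. The downside is small: additional modelling assumptions, and little gain from participants with baseline only. The model does not protect against loss that is not at random, and the SAP should say how it treats deaths before week 8.
- **(b) Keep the regression.** Correct 7.5 to say that the primary analysis uses participants with an observed week-8 outcome, analysed as randomised, and state the missingness assumption this needs. Word the secondary outcomes to match.

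Under either route, make one sensitivity analysis for missing outcomes (multiple imputation or delta shifts) fixed in advance, so that it is run whatever the missingness looks like. Confirm in the SAP that utilities after death are not imputed in the QALY analysis.

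The cost is protocol and SAP wording plus a modest amount of analysis. No new data are needed and the sample size does not change.
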